11.6.4. Duration of Response

Duration of response will be calculated for all responders from the date of the earliest assessment of CR or PR to the date of relapse or death, whichever occurs earlier, or the last disease assessment date for subjects without a relapse or death. Duration of SD will be calculated for subjects whose best response is CR, PR, or SD from the day study drug was first taken to the date of disease progression or death, whichever occurs earlier, or the last disease assessment for subjects without disease progression or death.

Duration of response and duration of SD will be summarized with descriptive statistics including arithmetic mean, standard deviation, median, and range will be summarized for subjects who have overall responses.

11.7. Safety Analyses

Safety will be assessed by subject-reported and investigator-observed Aes along with concomitant medications, Pes, clinical laboratory tests (hematology, coagulation, serum

chemistry, and urinalysis), vital signs, ECOG performance status, ECGs, and ECHO/MUGA scans.

All Aes will be mapped to the appropriate System Organ Class (SOC) and Preferred Term (PT) according to the Medical Dictionary for Regulatory Activities (MedDRA). Severity of Aes will be graded using CTCAE v4.03 (Appendix 2). All Aes collected during the study will be presented in data listings. TEAEs are defined as events that first occur or worsen after the subject receives study drug on C1D1 until 30 days after the last dose of study treatment, or the start of an alternative anticancer treatment, whichever occurs first, to be defined in more detail in the statistical analysis plan. Summaries will be provided by SOC and PT for all Aes, Aes considered related to study treatment, SAEs, and related SAEs as follows based on the treatment period when the events occur. Similar summaries will also be generated by maximum severity. In addition, exposure to ASTX029, reasons for discontinuation, deaths, and causes of deaths will be tabulated.

The number and proportion of subjects who have DLTs, as defined in Section 7.4, will be summarized by cohort and regimen in Phase 1 Part A.

Laboratory values reported by different local labs will be listed. Shift tables will be provided for each graded laboratory test.

Concomitant medications are the medications taken with a start date on or after the start of the administration of study treatment (C1D1) or those with a start date before the start of the administration of study treatment (C1D1) and a stop date on or after the start of study drug administration (C1D1) as to be defined in more detail in the statistical analysis plan. Concomitant medication will be coded by the World Health Organization (WHO) Global List and summarized by therapeutic subgroup (Anatomical Therapeutic Chemical [ATC] level 2) and PT, sorted alphabetically, using counts and percentages.

Vital sign measurements will be summarized by visit using the proportion of subjects with each vital sign being too high or too low according to conventionally accepted vital sign normal ranges. Physical examination, ECOG performance status, and ECG findings will be listed in data listings or analyzed with summary tables.

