Note: Other gene aberrations that in the investigator's opinion may confer sensitivity to ASTX029 may be included in Cohort F after obtaining approval from the Sponsor's medical monitor.

For each potential subject, there is an up to 21-day screening and eligibility assessment period before enrollment; the first dose of study treatment will be administered on Cycle 1 Day 1 (C1D1). Subjects will continue to receive their assigned treatments throughout the study until the occurrence of disease progression, death, or unacceptable treatment-related toxicity; they elect to discontinue study treatment or withdraw consent to continue study participation; or until the study is closed by the sponsor.

Study visits will take place weekly during Cycles 1 and 2 and less frequently thereafter (see Table 11 and Table 12 for the complete schedules of events for the Regimen 1 and Regimen 2, respectively). Serial blood samples will be collected for PK and biomarker analyses at specified time points. If a formalin-fixed paraffin-embedded (FFPE) archived tumor biopsy is available, it will be obtained for use in this study during screening. In addition, in Phase 1 Part A and Phase 2, fresh tumor biopsies are optional during screening and posttreatment during Cycle 2. In

Phase 1 Part B, fresh tumor biopsies are mandatory during screening and posttreatment during Cycle 2.

Upon permanent discontinuation of study treatment, there is a Treatment Termination (Tx Term) visit and a 30-day (± 5 days or within 3 days before starting new treatment) Safety Follow-up visit. Subjects who remain on study after the 30-day Safety Follow-up visit will be contacted periodically by telephone for collection of long-term health status information.

Tolerability and safety of study treatment will be evaluated throughout the study by collection of clinical and laboratory data. Antitumor response will be assessed according to standard Response Evaluation Criteria in Solid Tumors (RECIST) v1.1 using computed tomography (CT) or magnetic resonance imaging (MRI) scans. Subjects whose disease is not measurable using RECIST v1.1 will be evaluated using another appropriate method.

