7.3. Dose-Escalation Guidelines and Recommended Phase 2 Dose Decision

Dose-escalation/de-escalation decisions will be based on the occurrence of DLTs (defined in Section 7.4) during the first cycle of each dose level, and the recommendations of the DSRC following review of all available safety, PK, and biomarker data from the completed first cycle of at least 3 subjects in each cohort (Section 4.4). The DLT-based dose-escalation guidelines are summarized below.

Intrasubject escalations will not be allowed; however, once an MTD or RDE dose level is determined, active subjects may be allowed to receive their subsequent cycles at that dose level at the investigator's discretion with prior Sponsor approval.

First 3 Subjects in a Cohort

- If no subjects among the first 3 (<33%) experience a DLT, the dose may be escalated to the next higher level for the next cohort of 3 subjects.
- If 1 subject among the first 3 (33%) experiences a DLT, the cohort size will be increased to 6 subjects.
- If 2 subjects among the first 3 (>33%) experience a DLT, the previous dose level (ie, 1 step below) would be declared the MTD.

Expanded Cohort of 6 Subjects

- If no more than 1 subject in the cohort of 6 (ie, a total of 1 out of 6, <33%) experience a DLT, the dose may be cautiously escalated (~25% increase) to the next higher level for the next cohort of 3 subjects.
- If 2 subjects in the cohort of 6 (33%) experience a DLT, that dose level or the previous dose level (ie, 1 step below) would be declared the MTD for the regimen. The DSRC may recommend exploration of intermediate doses before an MTD is declared.
- If more than 2 subjects in the cohort of 6 (>33%) experience a DLT, the previous dose level (ie, 1 step below) would be declared the MTD for the regimen. The DSRC may recommend exploration of intermediate doses before an MTD is declared.

Recommended Dose for Expansion

The RDE is defined as either the MTD or a dose below the MTD that the DSRC agrees shows adequate safety, PK and/or preliminary biological activity, or clinical activity for a regimen. One or more dose levels (and regimens) may be studied in Phase 1 Part B to supplement available safety, PK, and/or clinical activity data and to evaluate target engagement in fresh tumor tissue biopsies. The RDE decision by the DSRC will be based on all available safety, PK, biomarkers, and preliminary activity data from all cycles (including potential for late or cumulative toxicity) from Phase 1 Part A.

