Recommended Phase 2 Dose

The RP2D is defined as the dose that the DSRC agree shows adequate safety, PK, pharmacodynamic, and/or biological or clinical activity to warrant further investigation in the Phase 2 part of this study. The RP2D decision by the DSRC will be based on all available PK, biomarker, safety, and preliminary clinical activity data from all cycles, including potential for late or cumulative toxicity from Phase 1 Parts A and B. The RP2D could be the same or lower than the RDE.

Based on the data presented in Section 1.3.3, the DSRC determined the RP2D to be 200 mg administered orally daily, continuously, in 21-day cycles under fasting conditions.

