#### 7.6.2 Adverse Events

Adverse events reported by study subjects or observed by investigators will be mapped to the appropriate System Organ Class (SOC) and Preferred Term (PT) according to the Medical Dictionary for Regulatory Activities (MedDRA). Severity of AEs will be graded using Common Terminology Criteria for Adverse Events (CTCAE) version 4.03 (protocol Appendix 2).

TEAEs are defined as events that first occurred or worsened on or after the date of the first dose of study treatment until 30 days after the last dose of study treatment or until the start of a post-treatment alternative anti-cancer treatment, whichever occurs first, with the following exceptions: events that occurred after 30 days beyond the last dose of study treatment or the start of a post-treatment alternative anti-cancer treatment will also be considered treatment-emergent if the events are both serious and related to the study treatment. For the purpose of determining whether an AE is a TEAE, incomplete AE start and stop dates will be imputed conservatively following the data programming conventions as detailed in the Taiho Data Programming Standards.

All AE data collected in the study database with an AE start date on or before the data cutoff date will be included in the data listings, including those that are not treatment emergent. Only TEAEs will be included in the AE summary tables.

An overall safety summary table containing counts and percentages of subjects with any AE, any AE Grade ≥3, AE leading to treatment discontinuation, any SAE, and subcategories of SAEs (fatal SAEs) will be produced.

Related events are those that the Investigator considered to be related to study treatment as described in the study protocol. All summaries of AEs will be summarized by cohorts and all cohorts combined within regimen within parts (A&B), and within Phase (I&II). Tables may be combined when space allows.

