## For example,

- Phase 1A: Cohort 1, Cohort 2, ..., Cohort n
- Phase 1B powder in bottle and tablets
- Phase 2: Cohort A, Cohort B, ..., Cohort F
- Phase 1A, Phase 1B, and Phase 2

The number and percentage of subjects experiencing AEs will be summarized by MedDRA SOCs (sorted alphabetically) with PTs sorted alphabetically within each SOC. The number and percentage of subjects experiencing AEs will also be summarized by PT and sorted by event frequency of the Total column. Related AEs, SAEs, and related SAEs will be summarized similarly. A summary of AEs with fatal outcomes, AEs resulting in permanent treatment discontinuation, and AEs resulting in treatment delay, interruption or dose reduction will also be provided. Additional summaries will be generated by SOC, PT and CTCAE grade. For these summaries, if the occurrence of a particular AE for a given subject is reported more than once, the event is only counted once with its worst CTCAE grade.

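### SAP 7.6.2 plans only crude adverse-event percentages over unequal exposure, so the report cannot show whether toxicity accumulates at the RP2D

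*Protocol*

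**What the plan says.** **Late toxicity as a stated concern.** Protocol 7.3 bases the RDE on "preliminary activity data from all cycles (including potential for late or cumulative toxicity) from Phase 1 Part A" and the RP2D on "data from all cycles, including potential for late or cumulative toxicity from Phase 1 Parts A and B". DLTs cover Cycle 1 only (Protocol 7.4, SAP 7.6.3).

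**AE summaries.** Protocol 11.7 lists summaries of AEs, related AEs, "SAEs, and related SAEs as follows based on the treatment period when the events occur". No list follows and the period is not defined. It also plans similar summaries by maximum severity. SAP 1.0 states that the SAP's analyses supersede those in the protocol. SAP 7.6.2 then says "All summaries of AEs will be summarized by cohorts and all cohorts combined within regimen within parts" and within phase. Tables are by SOC, PT and grade; where an event recurs in a subject, "the event is only counted once with its worst CTCAE grade". The Safety Analysis Set is everyone who received any study drug (SAP 5.4).

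**Exposure.** Protocol 4.1.2: "Subjects will continue to receive their assigned treatments throughout the study until the occurrence of disease progression" or another stopping reason. SAP 6.0 runs the analysis once all subjects have at least one RECIST assessment; the first on-treatment scan is at the end of Cycle 2 (Protocol 9.1, Table 11).

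**Related outputs.** SAP 7.6.1 tabulates dose intensity by cycle. All AEs are listed by subject. SAP 7.6.10 plans no analysis of ECHO/MUGA data.

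**The concern.** A percentage of all treated subjects counts in its denominator people who had already left treatment, or had not yet reached the later cycles at the cut, when a late event could have occurred. Two cohorts with the same risk per cycle will show different percentages if one stays on drug longer. A reader comparing cohorts, or asking what a patient faces by the sixth or eighth cycle, gets no answer from these tables.

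The question is a real one for this drug. Protocol 1.3.2.4 notes delayed skin lesions with ERK and MEK inhibitors. LVEF decrease is a named risk (Protocol 1.5 and Section 8), yet the first scheduled on-treatment ECHO/MUGA falls about two cycles in, after the DLT window. With no ECHO/MUGA analysis planned, the AE tables carry most of that signal.

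At stake is how safety at the RP2D is described in the study report.

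**Working it through.** **1. The plan's own safety figure.** Part B: 14 subjects, 15% incidence, stated 90% chance of at least one case (Protocol 11.1, SAP 4.0). 1 − 0.85^14 = 0.897, so the figure reproduces. It assumes that all 14 are at risk. For a late event with 15% risk among those still treated, if 7 of 14 remain (an assumption), the expected crude rate is 0.15 × 7/14 = 7.5%, and the chance of seeing one case is 1 − 0.85^7 = 67.9%.

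**2. Inputs for the size.** From the documents: 21-day cycles and a TEAE window of 30 days after the last dose, so w = 30/21 = 1.43 cycles. Assumed, because the documents give no figure: first-onset risk of 5% per cycle, so l = −ln 0.95 = 0.0513; exponential time on drug with median 2 or 4 cycles, so d = ln 2/median = 0.347 or 0.173.

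**3. Event that can start at any time.** Reference: risk over 8 cycles for a subject who stays on drug, 1 − 0.95^8 = 33.7%.
- Window ignored: crude = l/(l + d).
- Hazard continues through the whole window (an upper bound on the crude rate): crude = 1 − exp(−l·w) × d/(l + d).

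**4. Event that can start only after Cycle 2.** Reference: risk over the next 6 cycles on drug, 1 − 0.95^6 = 26.5%.
- Window ignored: crude = exp(−2d) × l/(l + d).
- Window included: crude = exp(−d(2 − w)) × l/(l + d).

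| Event | Median cycles | Crude, no window | Ratio | Crude, full window | Ratio |
|---|---|---|---|---|---|
| Any time (33.7%) | 2 | 12.9% | 2.6 | 19.0% | 1.8 |
| Any time (33.7%) | 4 | 22.8% | 1.5 | 28.3% | 1.2 |
| After Cycle 2 (26.5%) | 2 | 6.4% | 4.1 | 10.6% | 2.5 |
| After Cycle 2 (26.5%) | 4 | 16.2% | 1.6 | 20.7% | 1.3 |

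The ratios run from about 1.2 to 2.5 with the window and about 1.5 to 4 without it. The same 5% per cycle also gives crude rates of 12.9% or 22.8% (19.0% or 28.3% with the window) purely because exposure differs.

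**5. Dependence on retention.** For onset in Cycles 5 to 8 at 5% per cycle, the at-risk risk is 1 − 0.95^4 = 18.5%. With a fraction c of subjects discontinuing per cycle, crude = 0.05 × (1 − c)^4 × Σ[0.95(1 − c)]^k for k = 0 to 3 (window ignored). This gives 14.1%, 10.5%, 7.8%, 5.7% and 4.1% for c = 5%, 10%, 15%, 20% and 25%.

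**6. What the fix can support.** With a median of 2 cycles, a quarter of subjects enter Cycle 5 (0.5^2). That is 2.5 of 10 in a Stage 1 cohort and 3.5 of 14 in a Part B group. Pooled over six Stage 1 cohorts it is 15 of 60; at the planned Phase 2 maximum of about 180 it is 45.

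**The case against.** **The crude percentage is not wrong.** It estimates the share of treated subjects with an event, and the references of 8 and 6 cycles are chosen horizons. Under a median of 2 cycles only about 6% of subjects (0.5^4) are still on drug at 8 cycles. This stands: the gap is an unanswered question, not a biased estimate of the tabulated quantity.

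**A reader might infer that the SAP drops promised by-period tables and hides the change.** The documents do not establish this. Elsewhere the protocol uses *treatment period* for time on drug (5.2, 7.1.5, Table 13), and restricting tables to TEAEs would satisfy that reading. If a dose or cohort period is meant, SAP 7.0 groups AEs by assigned cohort at onset, although SAP 5.4 fixes treatment at Cycle 1 Day 1 while Protocol 7.3 lets subjects move to the MTD or RDE. The term needs defining; an undeclared deviation is not shown.

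**A reader might infer that counting once at worst grade hides late toxicity.** It does not: a late first event, or a late worsening, is counted. The rule agrees with the protocol's maximum-severity summaries. What is lost is timing, recurrence and persistence.

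**A reader might infer that the RP2D rests on these tables.** It does not. Protocol 7.3 records that "the DSRC determined the RP2D to be 200 mg administered orally daily", and Protocol 11.3 has DSRC reviews supported by ongoing analyses.

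**Other outputs help.** Exposure duration, dose reductions and delays by cycle, laboratory shifts, vital signs by visit and full listings are planned, and table specifications sit in a separate document not available here. These give partial evidence, but none described in the SAP pairs AE onset with an at-risk denominator.

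**Conclusion.** The concern holds in a limited form. The AE tables described in SAP 7.6.2 mix unequal exposure within and between cohorts, understate the risk for subjects who remain on drug, and cannot show whether toxicity accumulates, although the protocol names that as a concern.

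The size is illustrative. It rests on an assumed constant 5% first-onset risk per cycle, exponential time on drug with a median of 2 to 4 cycles, and horizons of 8 or 6 cycles. On those assumptions the understatement is about 1.2- to 2.5-fold with the hazard running through the 30-day window, and 1.5- to 4-fold with the window ignored; the truth under the model lies between. Actual retention could move it either way.

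The consequence is for reporting and interpreting safety at the RP2D. Neither a flawed dose choice nor a concealed departure from the protocol follows. This is a cheap improvement worth making.

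**What to change.** In SAP 7.6.2:

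1. Add one table for all subjects treated at the RP2D, pooled, and per cohort only where numbers allow. Show TEAEs, related TEAEs and Grade 3 or higher TEAEs by interval of first onset: Cycle 1, Cycles 2 to 4, Cycle 5 onward. Use as denominator the subjects treated in that interval and still free of the event. State that an event starting after the last dose but inside the TEAE window belongs to the interval of the last dose.
2. Add a summary of time to first related Grade 3 or higher TEAE, censored at the end of the TEAE window or the data cut, whichever is earlier.
3. State what *treatment period* in Protocol 11.7 means for AE summaries, and record the additions in SAP 7.9.

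The cost is one table and one time-to-event summary from AE and dosing dates already collected. Late intervals will have small denominators, which is why three intervals and pooling are preferable to a finer split by cohort. Subjects still treated in late cycles are also a selected group who tolerated the drug, so the late rates should be described as conditional on remaining on treatment.

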11.8. Pharmacokinetic Analyses

The PK Analysis Set (Section 11.2.4) will be used for PK analyses.

The PK parameters will be derived for each subject using a noncompartmental approach. Descriptive statistics including mean, standard deviation, median, and range for PK parameters for ASTX029 will be summarized separately for each regimen and by dose within each regimen. Detailed and additional PK analyses are described in a separate PK analysis plan.

11.9. Pharmacodynamic/Biomarker Analyses

The Pharmacodynamic and Biomarker Analyses Set (Section 11.2.5) will be used for pharmacodynamic and biomarker analyses.

Values at baseline and changes from baseline (if appropriate) of the pharmacodynamic parameters and biomarkers assessed in the study will be summarized descriptively using mean, standard deviation, median, minimum, and maximum for continuous variables and counts and

percentages for categorical variables. Summaries will be provided separately for each regimen in Phase 1 Part A, for the RDE cohort(s) in Phase 1 Part B, and for each cohort in Phase 2.

11.10. Interim Analysis

No interim analysis is planned for this open-label study. The data will be reviewed in an ongoing manner in conjunction with dose-escalation decisions and general safety monitoring.

11.11. Procedures for Handling Missing, Unused, and Spurious Data

No imputation of values for missing data will be performed unless specified otherwise in the statistical analysis plan. Data from subjects lost to follow-up will be included in statistical analyses to the day of last contact.

12. STUDY DURATION AND TERMINATION

The expected study duration is approximately 5 years (61 months), including approximately 55 months for recruitment and approximately 6 months for safety follow-up.

The Sponsor may stop the study at any time. In case of this event, the Sponsor will make reasonable efforts to ensure subjects are transitioned off study in an orderly manner. Reasons for early termination include, but are not limited to, lack of preliminary clinical activity or safety concerns.

13. STUDY COMPLIANCE AND ETHICAL CONSIDERATIONS

13.1. Compliance Statement

The study will be conducted in accordance with the ICH GCP guidelines, principles enunciated in the Declaration of Helsinki, and all human clinical research regulations in countries where the study is conducted.

13.2. Informed Consent

The ICFs used for the study must comply with the Declaration of Helsinki, federal regulations US 21 Code of Federal Regulations (CFR) Part 50, and ICH GCP guidelines and any other local regulations. The investigator, or a person delegated by the investigator, must explain the medical aspects of the study, including the nature of the study and the treatment, orally and in writing, in such a manner that the subject is aware of potential benefits and risks. Subjects must be informed that participation is voluntary and that they may withdraw from the study at any time, without prejudice. Subjects, or a legal guardian if the subject is unable to, must give informed consent in writing.

The informed consent process must be conducted, documented in the source document (including the date), and the form must be signed, before the subject undergoes any study-specific procedures.

13.3. Institutional Review Board or Independent Ethics Committee (IRB/IEC)

The investigator must submit the protocol, protocol amendments, and the ICF for the proposed study, along with any other documents required by the center's IRB/IEC to the center's duly constituted IRB/IEC for review and approval. The investigator must also ensure that the IRB/IEC reviews the progress of the study on a regular basis and, if necessary, renews its approval of the study on an annual basis. A copy of each IRB/IEC approval letter must be forwarded to the sponsor before the study is implemented. Documentation of subsequent reviews of the study must also be forwarded to the sponsor.

